F1	SAMPLE SIZE DETERMINATION AND POWER	19
F2	INTERIM MONITORING AND EARLY STOPPING.....	19
F3	ANALYSIS PLAN	19
F4	MISSING OUTCOME DATA.....	20
F5	UNBLINDING PROCEDURES	20
G	DATA HANDLING AND RECORD KEEPING	20
G1	CONFIDENTIALITY AND SECURITY	20
G2	RECORDS RETENTION	20
H	STUDY ADMINISTRATION	20
H1	PARTICIPANT PAYMENT	21
H2	STUDY TIMETABLE	21
I	PUBLICATION PLAN	21
J	ATTACHMENTS	22
J1	INFORMED CONSENT DOCUMENTS	22
J2	PATIENT EDUCATION BROCHURES	22
J3	QUESTIONNAIRES OR SURVEYS.....	22
K	REFERENCES	22

A Introduction

A1 Study Abstract

Introduction: Snoring is a problem affecting nearly 40% of the adult population and which leads to adverse health outcomes in the participant and sleeping partner. Despite the large number of people affected, insufficient research exists in the published medical literature documenting treatment effectiveness for primary snoring. Contrary to this, a large amount of research exists on effective treatment for sleep apnea; from this comes our understanding of the treatment effectiveness for snoring. The goal of this study is to determine whether Mandibular Advancement Devices (MAD) are an effective treatment for primary snoring when compared to conservative therapies.

Methods: This study will consist of a randomized control trial of adult participants with non-apneic snoring. Participants will be recruited from an academic medical center and randomized into either conservative therapy that is medicated nasal rinses, external nasal dilator, mouth taping, and lateral positional therapy or Mandibular Advancement Device. Participants and their sleeping partner will be evaluated at baseline and at follow up with a modified Clinical Global Impression (CGI) Scale. At baseline, they will be evaluated with a CGI-Severity scale, and at follow up with a CGI-Improvement scale. The primary outcome is the Snoring Clinical Global Impression Scale-Improvement for the sleeping partner. Secondary outcomes include change in the Epworth Sleepiness Scale (ESS) in the participant, change in ESS in the sleeping partner, CGI-I Scale for the participant, change in the SNORE25 for the participant, and change in SNORE25 for the sleeping partner.

A2 Primary Hypothesis

We hypothesize that the Mandibular Advancement Device (MAD) will result in a clinically meaningful, statistically significant difference in the modified Snoring CGI-I Scale when compared to the conservative therapy for participants with non-apneic snoring as measured by their sleeping partner.

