3. **Epworth Sleepiness Scale (ESS) - Partner and Participant:** The ESS is a commonly used measure to evaluate the propensity to of a participant to fall asleep in 8 everyday scenarios “in recent times”. The participant rates each situation on a scale of 1-7, with 1 being least likely to fall asleep and 7 being the most likely²². When used as an outcome, the ESS shows similar outcomes for participants with sleep apnea when compared to CPAP²⁰. De Meyer et al. conducted a systematic review of studies looking at the minimal clinically important difference (MCID) of the ESS, and found a range between 2 and 3. It calculated the exact MCID as being 2.4, and found the scale has a good internal and external validity²³. As a conservative value, we will use 3 as the MCID in this study. The ESS will be collected both at the baseline and at follow up, and a change in the ESS will be calculated.
4. **Symptoms of Nocturnal Obstruction and Related Events (SNORE-25) - Partner and Participant:** The SNORE-25 is a modification of the Obstructive Sleep Apnea Patient-Oriented Severity Index (OSAPOS) which includes 25 total items of symptoms with possible scores ranging from 0 to 5, with high scores indicating greater sleep-disordered breathing—related health burden²⁴. For the sleeping partner, we will administer a modified form of the SNORE-25 which preserves the intent of each of the questions but changes the wording to refer to effects of the participants snoring on the sleeping partner’s life.
5. **Pittsburgh Sleep Quality Index (PSQI) - Partner and Participant:** The PSQI is a self-rate questionnaire which assess sleep quality and disturbances over a 1-month time interval. It is composed of 19 items which contribute to 7 different component scores: Subjective sleep quality, sleep latency, sleep duration, habitual sleep efficiency, sleep disturbances, use of sleeping medication, and daytime dysfunction. A global sum of these components > 5 signifies poor sleep quality with a sensitivity of 89.6% and a specific of 86.5%²⁵. The PSQI will be taken at baseline and at follow up.

D Study Design

D1 Overview

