At the baseline study visit, The RC or RA and the participant and sleeping partner will complete the demographic information and baseline measures. This includes the baseline CGI-S scale, the ESS, and the SNORE-25 or the modified SNORE-25. Then randomization of the participant will occur. Participants randomized to the MAD will be scheduled to meet with the maxillofacial physician, ideally within two weeks of randomization, to be fit with the MAD. Participants randomized to the conservative therapy will be given a roll of Johnson and Johnson Band-Aid Woven Adhesive Bandages 1" x 3", one box of Breath-Right strips (either small, medium, or large), and one Neti-Pot. The participants will receive their topical glucocorticoid prescription through the mail from AdvancedRx.

E4 Maxillofacial Visits

Participants randomized to the Mandibular Advancement Device arm of the trial will undergo additional visits with the Maxillofacial Physician. The first visit will be setup after the baseline study visit to occur within 2 weeks of the consent process. At the first visit, the maxillofacial physician will educate the participant on the device, explain the treatment plan to the participant, and take a molding of the participant's teeth at this meeting. After this, the molding and measurements will be sent to ProSomnus to have the device made, which will take 7-10 days. Once the device is received by the Maxillofacial office, a second meeting will occur. At this meeting, the maxillofacial physician will ensure the device is correct size and shape and will not create undue pain or discomfort, review proper use of the device, including self-titration of the degree of jaw protrusion, and proper care of the device. These meetings will occur during the 4-week pre-intervention period as outlined in section F2.

E5 Daily Check-ins

Every morning the sleeping partner will receive a text message asking them to complete the CGI-S for the sleeping partner (*CGI-S Sleeping Partner*). They will respond via their telephone to the single question prompt until the end of the study.

E6 Visit 2

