At the end of study, all the Visit 2 - End of Study outcome measures will be presented to the participant via REDCap. The End of Study measures include the CGI-I scales, the CGI-S scale, the ESS, and the SNORE-25 or modified SNORE-25. This will occur asynchronously through email surveys distributed through the Washington University REDCap server or through a scheduled telephone call depending on the participant's preference. Both the participant and the sleeping partner will complete this step. Participants will also return their compliance sheets at this time.

E7 Safety and Adverse Events

7.a Safety and Compliance Monitoring

The specific monitoring plan for this study is based on the potential risk of participation and size and complexity of the planned investigation. Based on these considerations, this study will have a monitoring committee comprised of [name], [name], and [name], the study biostatistician. All reports of a Serious Adverse Event (SAE) or an Unexpected Adverse Event (UAE) will be investigated by the monitoring team and reported to Washington University HRPO according to the reporting requirements.

Participants who experience serious adverse effects with therapy will be removed from the study. Participants with serious adverse effects will be instructed to call 911, seek immediate medical care and discontinue all further treatment.

7.b Definitions of Adverse Events

Adverse event (AE) means any untoward medical occurrence associated with the use of a drug in humans, whether or not considered drug related (21 CFR 312.32(a)).

An adverse event (also referred to as an adverse experience) can be any unfavorable and unintended sign (e.g., an abnormal laboratory finding), symptom, or disease temporarily associated with the use of a drug, without any judgment about causality or relationship to the drug.

An adverse event can arise from any use of the drug (e.g., off-label use, use in combination with another drug) and from any route of administration, formulation, or dose, including an overdose.

Serious adverse events (SAEs) are special cases of an adverse event where adverse outcomes are severe. SAEs include the following events:

- Death of any of the participants associated with a clinical trial.
- An event which can lead to life-threatening complications or put the life of participants at risk because of participation in a clinical trial.

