95% confidence interval around the difference will be calculated and reported. Chi square test or Fisher's exact test will be used to compare categorical level outcomes between the 2 study groups, including the difference in Responder Rate. Effect sizes and 95% CIs will be reported for each comparison. For secondary outcomes, independent samples t-test or its non-parametric equivalent Mann-Whitney U test will be used to compare continuous level outcomes between the 2 study groups. Median or mean difference and CI will be calculated and reported according to the test being used. The role of potential confounders will be explored in multivariate analysis using logistic regression or GLM. All statistical analyses will be conducted in SPSS 28 (IBM Corp., Armonk, NY).

F4 Missing Outcome Data

All attempts will be made to minimize the occurrence of missing outcome data through adherence to the principles of Good Clinical Practice and the reduction of the complexity and number of assessments. It is assumed that all missing data will be at random. As this is a small pilot study, no computational techniques will be employed to adjust analyses for missing data.

F5 Unblinding Procedures

After all data analysis and charts, tables, and graphs are created, unblinding will occur. [name] will break the blind and all placeholders in the manuscript and graphics will be replaced with the corresponding intervention.

G Data Handling and Record Keeping

G1 Confidentiality and Security

Procedures are in place to curb risks of breaches in confidentiality and privacy. These procedures include: 1) formal training protocols centered on the maintenance of confidentiality for all study team members; 2) a password-protected computer file that contains the identity of participants, corresponding ID numbers, and contact information; 4) secure storage for identified data forms such as completed questionnaires; and 5) communication with study team via secure email, phone line, or tele-video call.

Only members of the study team will have access to the electronic research files. All research data files will be stored on secure Washington University servers with computer, network, and database-level passwords that will only be accessible to study team members. No participant identifying information will be revealed in any publications or presentations.

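### F3 compares ESS and SNORE-25 change scores without adjusting for the baseline score; naming a baseline-adjusted main estimate would be a low-cost precision gain for these secondary outcomes

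*Combined protocol and SAP*

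**What the plan says.** F3 plans that an "independent samples t-test or its non-parametric equivalent Mann-Whitney U test will be used to compare continuous level outcomes between the 2 study groups", with the matching mean or median difference and its confidence interval. F3 does not say whether the compared quantity is the follow-up score or the change; that comes from earlier sections. The abstract (A1) lists "change in the Epworth Sleepiness Scale (ESS) in the participant, change in ESS in the sleeping partner" and "change in the SNORE25 for the participant, and change in SNORE25 for the sleeping partner" among the secondary outcomes, and C3 says of the ESS: "The ESS will be collected both at the baseline and at follow up, and a change in the ESS will be calculated".

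The baseline scores exist before allocation. E3 has participant and partner complete the baseline measures at Visit 1: "This includes the baseline CGI-S scale, the ESS, and the SNORE-25 or the modified SNORE-25". The next sentence is "Then randomization of the participant will occur". E6 collects the same instruments again: "The End of Study measures include the CGI-I scales, the CGI-S scale, the ESS, and the SNORE-25 or modified SNORE-25".

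The only covariate modelling in F3 is an exploratory logistic regression or GLM for confounders that are not named. It neither mentions the baseline score nor makes an adjusted result the reported estimate.

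**The concern.** Subtracting the baseline fixes its coefficient at 1. When the correlation between visits is moderate, that is too large a correction and it adds noise to the treatment comparison. A linear model that estimates the coefficient usually gives a tighter interval from the same data. F1 justifies the sample by the width of an interval, and F3 promises effect sizes with 95% intervals throughout, so interval width is a large part of what this pilot will deliver on ESS and SNORE-25. The partner analyses serve secondary aim C2, which concerns the sleeping partner. The participant analyses serve the secondary outcomes listed in A1 and C3.

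**Working it through.** **Inputs from the documents.** 60 snorers randomised 1:1, 33% dropout, 40 evaluable, 20 per arm (F1 and D3 section 3.c). F1 counts snorers only; the same number of evaluable partners is assumed.

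**Assumptions.** The documents give neither a standard deviation (SD) for ESS or SNORE-25 nor the correlation r between baseline and follow-up. I take r = 0.3 to 0.9, baseline SD = 1, and k = follow-up SD / baseline SD, with k = 1 unless stated.

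**The plan's own precision figure.** F1 states a margin of 30% for the responder difference at 20 per arm, with rates of 30% and 50%: 1.96 × √(0.30×0.70/20 + 0.50×0.50/20) = 0.297. It reproduces. No such figure is given for ESS or SNORE-25.

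**Formulas, n per arm.**
- Change score: variance = 1 + k² − 2rk; half-width = t(2n−2) × √(variance × 2/n).
- Adjusted: variance = k²(1 − r²) × [1 + 1/(2n−4)], where the bracket is the expected cost of estimating the slope; half-width = t(2n−3) × √(variance × 2/n).

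At n = 20: t = 2.024 and 2.026; bracket = 1 + 1/36 = 1.028.

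Example, r = 0.5, k = 1. Change: 2.024 × √(1.00 × 0.1) = 0.640. Adjusted: 2.026 × √(0.75 × 1.028 × 0.1) = 0.563. Ratio 0.879.

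| r (k = 1, n = 20) | Change half-width (SD) | Adjusted half-width (SD) | Ratio | Narrower by |
|---|---|---|---|---|
| 0.3 | 0.757 | 0.620 | 0.818 | 18% |
| 0.5 | 0.640 | 0.563 | 0.879 | 12% |
| 0.7 | 0.496 | 0.464 | 0.936 | 6% |
| 0.9 | 0.286 | 0.283 | 0.989 | 1% |

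Simulation with normal data (40,000 trials per setting) gave mean ratios within 0.003 of the formula and coverage of 94.7 to 95.1% for both methods. The adjusted interval was the narrower one in 99, 96, 85 and 52% of trials at 20 per arm.

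**Fewer evaluable cases (assumed 10 per arm).** Ratios 0.835, 0.896, 0.954 and 1.009.

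**Unequal SDs, n = 20, same four r.** k = 0.7: 0.655, 0.692, 0.710, 0.646. k = 1.3: 0.911, 0.969, 1.010, 0.972.

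**Worst expected loss against the t-test on change.** The change variance exceeds k²(1 − r²) by (1 − rk)², which is never negative, so the worst case is rk = 1, where only the small-sample cost remains. At n = 20: √1.028 × 2.026/2.024 = 1.015, a loss of 1.5%. At n = 10: √1.0625 × 2.110/2.101 = 1.035, a loss of 3.5%.

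**Strong skew, both directions.** Lognormal scores with log-scale SD 1, an assumed shift of 0.8 on the log scale, 20 per arm; power at r = 0.3 / 0.5 / 0.7:

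| Shift | Linear adjusted model | Mann-Whitney U on change |
|---|---|---|
| Downward | 51 / 57 / 71% | 36 / 46 / 65% |
| Upward | 52 / 56 / 71% | 57 / 68 / 86% |

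The ordering reverses with the direction of the shift. The 1.5% bound therefore does not extend to Mann-Whitney U.

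**Divergence in the analysed set.** The change estimate subtracts the whole baseline gap between arms and the adjusted estimate subtracts rk times it, so they differ by (1 − rk) × gap. An assumed gap of 0.3 SD at r = 0.5, k = 1 gives 0.5 × 0.3 = 0.15 SD, about twice the half-width saved (0.640 − 0.563 = 0.077 SD).

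**The case against.** The strongest reply is that nothing here is an error. A t-test or Mann-Whitney U on change is conventional and valid under randomisation, F1 describes a pilot sized on feasibility, and no precision target for ESS or SNORE-25 is missed. That stands, and it is why the point is of low severity.

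F3 also foresees a GLM, which could include the baseline score. True, but its covariates are unnamed and its role is exploratory, so no adjusted estimate is fixed in advance.

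The size of the gain rests on assumed values. This stands too: across the settings shown at 20 per arm, the result runs from 35% narrower to 1% wider. What survives is the asymmetry against the t-test, whose worst expected loss is 1.5%. Against Mann-Whitney U under strong skew there is no such assurance, and the documents do not give the shape of the scores. That is the reason to keep the rank test.

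Finally, F3 uses a per-protocol set and D2 section 2.i leaves withdrawn participants' data out of the analysis, so baseline balance between the compared groups is not assured. The two estimates may then differ by more than precision. This stands and belongs in the plan.

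A reader might infer that the planned comparison is biased, or that adjustment would repair selection in the per-protocol set. The documents support neither. Change scores already take the baseline into account, and under either method the compared groups are not the full randomised groups.

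**Conclusion.** The point holds as a low-severity improvement to four secondary analyses: ESS and SNORE-25, each for participant and partner. Under equal SDs and 20 evaluable per arm, the adjusted interval is about 18, 12, 6 or 1% narrower than the change-score t-test interval at r = 0.3, 0.5, 0.7 or 0.9. The actual gain is unknown and would be negligible near r = 0.9. It would be wrong to read this as strengthening the main result: the primary outcome is the partner's CGI-I response, which is rated only after treatment and has no baseline counterpart, and the sample size is unaffected.

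**What to change.** Before analysis begins, state in F3 that the main estimate for ESS and for SNORE-25, separately for participant and partner, is the treatment difference with 95% interval from a linear model of the follow-up score on arm and that instrument's own baseline score. Keep the planned t-test or Mann-Whitney U as a prespecified supportive analysis. Add that baseline balance is not assured in the per-protocol set, that the adjusted and change-score estimates may therefore differ by more than precision, and that the adjusted estimate is the one to be interpreted.

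PSQI could follow once its schedule is reconciled: C3 says "The PSQI will be taken at baseline and at follow up" and E8 lists it after the intervention, but the visit lists in E3 and E6 omit it. CGI-S, a single item with five categories, is left out of this change.

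The cost is wording, plus one degree of freedom per model. Both instruments are already collected at both visits, F3 already names GLM, and no extra visit or participant is needed.
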